#### **6.4. Subset Analyses**

There are no planned subset analyses.

## 6.5. Baseline and Other Summaries and Analyses

#### 6.5.1. Demographic Summaries

Demographic characteristics will be summarized for enrolled population in accordance with with the sponsor reporting standards.

#### 6.5.2. Study Conduct and Participant Disposition

Participants evaluation groups will show end of study participant disposition. Frequency counts will be supplied for participant discontinuation(s) by treatment. Data will be reported in accordance with the sponsor reporting standards.

#### **6.5.3. Study Treatment Exposure**

Study treatment exposure will be listed.

#### 6.5.4. Concomitant Medications and Nondrug Treatments

All concomitant medication(s) as well as non-drug treatment(s) will be reported in the listings according to current sponsor reporting standards.

#### 6.6. Safety Summaries and Analyses

All safety analyses will be performed on the Safety Analysis Set.

Safety data will be presented in tabular and/or graphical format and summarized descriptively, where appropriate.

#### 6.6.1. Adverse Events

Adverse events will be reported in accordance with the sponsor reporting standards.

Participant discontinuations due to adverse events will be detailed by treatment. Data will be reported in accordance with the sponsor reporting standards.

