3. OBJECTIVES AND ENDPOINTS

Objectives	Endpoints
P1imary:	Primary:

 To characterize the safety and tolerability of multiple oral doses of sisunatovir in healthy adult participants 	
 Assessment ofTEAEs, clinical laboratory abnormalities, vital signs, and 12-lead ECGs
Secondary:	Secondary:

 To characterize the PK of multiple oral doses of sisunatovir To evaluate the effect of food on the PK of multiple oral doses sisunatovir To characterize the impact ofliquid vehicles on the palatability of sisunatovit- 	
 PK Parameters AUCtau, Cmax., Tmax, AUCtau(dn), Cmax(dn) for Day 1 and AUCtau, Cmax, Tmax, AUCtau(dn), Cmax(dn), CL/F, Rac, Rac,Cmax; and t112 and V,/F (if data penuits) post last dose on Day 5 The ratio of AUCtau and Cma...,on Day 5; Tmax on Day 5 Palatability Assessment Questionnaire Scoring Metrics: mouth feel, bitterness, sweetness, sourness, saltiness, tongue/mouth burn, overall liking
CCI	
■ [REDACTED]	■ [REDACTED]

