4.2. Scientific Rationale for Study Design

The primary purpose of this study is to assess the safety and tolerability of 400 mg sisunatovir when dosed Q12 hours for 4 days plus 1 dose. In a clinical study evaluating the effect of sisunatovir on RSV viral load following a viral challenge in healthy participants indicated that both 200 and 350 mg Q12 for 5 days robustly decreased viral load relative to placebo (C5241002). The effect at the 350 mg dose was numerically superior to the 200 mg dose; however, the 350 mg dose was associated with GI-related AEs, which was also consistent with data from the MAD study (C5241001) indicating an increase in GI AEs at higher doses, the majority of GI-related AEs were mild. Since sisunatovir was dosed in the fasted state in these studies, it is not known if food will ameliorate these GI AEs. To fill this knowledge gap, the first 2 periods of Cohort 1 are designed to assess the safety and tolerability of 400 mg Q12 hours (n=12) versus 200 mg Q12 hours (n=6) and placebo (n=6). As a secondary objective, the effect of food on the safety, tolerability and PK of sisunatovir at the 400 mg Q12 hours dose will be compared. Thus, the data from the first 3 periods of Cohort 1 are designed to assess the highest well-tolerated dose of sisunatovir that can be assessed in future clinical studies and if food can ameliorate any potential GI AEs.

Since the projected exposure at the 400-mg dose is expected to provide approximately 1.2x margins for AUC and Cmax using the rat NAOEL as the most sensitive species, the PK from each of Period 1 and Period 2 will be assessed prior to dosing the subsequent period. If the Day 5 exposure at the 400-mg dose exceeds the rat NOAEL (most sensitive species), then the dose in subsequent periods will be capped at a dose that is not projected to exceed the rat NOAEL. Note doses in Periods 2 and 3 may be adjusted based on safety findings from the previous dosing periods (see [Section 4.1](#)).

Optional Cohort 2 is included and will only be conducted at the discretion of the sponsor after reviewing data from at least the first 2 periods of Cohort 1. This cohort could potentially be used to collect data at a lower dose (e.g., 300 mg) or collect additional data at a dose that does not exceed 400 mg Q12 hours, depending on the exposures observed in Cohort 1.

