The primary purpose of Cohort 1 of this study is to evaluate the safety and tolerability of the 400 mg Q12 hours x 4 days plus one dose dosing regimen and if any potential GI AEs can be mitigated with food. Therefore, within the first 2 periods of Cohort 1, each participant will receive 400 mg Q12 hours x 4 days plus 1 dose of sisunatovir with food (compared to placebo or 200 mg Q12hours). In Period 3 of Cohort 1, participants will receive 400 mg Q12 hours x 4 days plus 1 dose fasted to directly compare PK, safety and tolerability in the same participants dosed fed at the same dose level. Note doses in Periods 2 and 3 may be adjusted based on PK and safety findings from the previous dosing periods (see [Section 4.1](#)).

The effect of food on the pharmacokinetics of sisunatovir has been variable in Phase 1 studies. However, the effect of food on the pharmacokinetics of sisunatovir using the formulation to be used in this study (dry powder blend in capsules) showed minimal food effect.

As the exposure of sisunatovir increases in a greater than dose proportional manner, the steady state exposure at the planned dose in Cohort 1 (400 mg Q12 hours) is expected to be ~40% greater than the exposure at the highest dose studied to date (350 mg Q12 hours). At this dose, the anticipated safety margin over rat (most sensitive species) NOAEL AUC and C_{max} in the 28-day toxicology study are 1.2-fold.

Cohort 2 in this study is optional and will only be conducted at the discretion of the sponsor after reviewing data from Cohort 1. The dose assessed in Cohort 2 will not exceed 400 mg Q12 hours x 5 days or a dose that is projected to exceed the rat NOAEL based on Cohort 1 PK data. This cohort may be used to assess a lower dose (e.g., 300 mg) or may be used to collect additional data at the same dose that has been tested in Cohort 1 and is viewed as safe. These data may then be used to define the dose and dosing instructions in Phase 2/3.

The dose for the palatability cohort (50 mg in a 7 mL dosing solution) was selected to be close to the anticipated drug concentration in pediatric studies.

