6.4. Blinding

The first 2 periods of each cohort are double blind (sponsor open) design.

Study intervention administrated in Periods 3 to 7 of the study will be open to the participant, Investigator and Sponsor or Sponsor-designate personnel responsible for study monitoring activities (including all site monitoring activities).

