## 2.2. Study Objectives, Endpoints, and Estimands

The following are the objectives and endpoints in this study. Estimand framework will not be applied to this Phase 1 study in healthy participants.

Objectives	Endpoints
Primary:	Primary:
• To characterize the safety and tolerability of multiple oral doses of sisunatovir in healthy adult participants	Assessment of TEAEs, clinical laboratory abnormalities, vital signs, and 12-lead ECGs
Secondary:	Secondary:
To characterize the PK of multiple oral doses of sisunatovir	• PK Parameters AUC tau , C max , T max , AUC tau (dn), C max (dn) for Day 1 and AUC tau , C max , T max , AUC tau (dn), C max (dn), CL/F R ac , R ac,Cmax ; and t 1/2 and V z /F (if data permits) post last dose on Day 5
• To evaluate the effect of food on the PK of multiple oral doses of sisunatovir	• The ratio of AUC tau and C max , on Day 5; T max on Day 5
To characterize the impact of liquid vehicles on the palatability of sisunatovir	Palatability Assessment Questionnaire Scoring Metrics: mouth feel, bitterness, sweetness, sourness, saltiness, tongue/mouth burn, overall liking
CCI	

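### Protocol 4.2 and 4.3 say Cohort 1 will show whether food mitigates GI AEs at 400 mg in the same participants, but no objective, GI outcome or paired analysis follows, and the AE attribution rule gives fed and fasted unequal windows

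*SAP*

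**What the plan says.** **Purpose.** Protocol 4.3 describes the primary purpose of Cohort 1 as evaluating the 400 mg regimen and "if any potential GI AEs can be mitigated with food". It says Period 3 is there to "directly compare PK, safety and tolerability in the same participants dosed fed at the same dose level". Protocol 4.2 says the same of the first three periods and introduces the comparison with "As a secondary objective, the effect of food on the safety, tolerability and PK of sisunatovir".

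**Objectives tables.** In Protocol 3 the only food objective is "To evaluate the effect of food on the PK of multiple oral doses sisunatovir". SAP 2.2 matches it: "To evaluate the effect of food on the PK of multiple oral doses of sisunatovir". The primary objective in both is general and does not mention food: "To characterize the safety and tolerability of multiple oral doses of sisunatovir in healthy adult participants".

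**Analysis.** Every fed-versus-fasted estimate in the SAP is PK. SAP 6.2.2 has the A against D mixed model and individual ratios for AUCtau and Cmax, and SAP 3.2.2 has a Hodges-Lehmann estimate for Tmax. For AEs, SAP 6.6.1 states "Adverse events will be reported in accordance with the sponsor reporting standards" and adds only that discontinuations due to AEs are detailed by treatment. SAP 5.2 says by-treatment summaries will cover dose and fed/fasted condition where applicable, and Protocol 9.3.1 reports all arms separately.

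**Attribution.** SAP 3.5.1 assigns washout events to the previous treatment and follow-up events to the last treatment taken.

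**Order and blinding.** A is given blinded in Period 1 or 2. D is always Period 3, and Protocol 6.4 says: "Study intervention administrated in Periods 3 to 7 of the study will be open to the participant, Investigator and Sponsor".

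**The concern.** The question that justifies the within-participant design has no formal objective, no defined outcome and no planned comparison. What the SAP foresees is a count for A and a count for D. Two such counts do not show whether the same people had GI events in both conditions, and they carry no interval. Different paired results can lie behind one table and support different conclusions about food.

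The two counts are also not collected over the same time. Following SAP 3.5.1 as written, A has a longer period after dosing in which an event is charged to it. Any late GI events would be over-represented under fed dosing, which would tend to understate a benefit of food.

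At stake is whether the report can answer the tolerability question that Protocol 4.2 and 4.3 pose, or leaves the reader to infer it from two unequal tallies.

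**Working it through.** The plan states no figure for this comparison: there is no GI AE rate, effect size or power. The Cohort 1 size is consistent: 4 sequences × 3 participants = 12, so at most 12 A/D pairs before dropout.

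**1. Attribution windows in Cohort 1**

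Inputs: the last dose is the morning of Day 5, 96 hours after the first (Protocol 1.3). Washout is at least 7 days from last dose to next first dose (Protocol 4.1). Periods 4-7 take place on Day 7 of Period 3, at least 48 hours after its last dose (Protocol 1.3 and 4.2). Events go to the treatment most recently taken (SAP 3.5.1).

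- A: 96 h of dosing + at least 168 h of washout = at least 264 h.
- D: 96 h of dosing + about 48 h = about 144 h. Later events pass to a palatability treatment.
- Ratio: 264/144 = 1.8 or more.

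**2. What separate counts leave out**

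Assumed for illustration, since the documents give no rates: at least one GI TEAE in 6/12 fasted and 2/12 fed. Let b = participants with events fasted only, c = fed only, n = 12. The paired difference is (b − c)/n = 4/12 = 33 points in every case below.

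The 90% score (Tango) interval is the set of Δ for which |b − c − nΔ| / √{n[2q + Δ(1 − Δ)]} ≤ 1.645. Here q is the constrained estimate of the fed-only probability: q = [√(B² − 4AC) − B]/(2A), with A = 2n, B = −b − c + (2n − b + c)Δ and C = −cΔ(1 − Δ).

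| Participants with events in both | b v c | 90% score CI |
|---|---|---|
| 2 | 4 v 0 | 8.8% to 56.9% |
| 1 | 5 v 1 | -0.3% to 59.8% |
| 0 | 6 v 2 | -5.6% to 62.7% |

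Check of one limit (4 v 0, Δ = 0.088): q = 0.0933, the variance term is 12 × [0.1866 + 0.088 × 0.912] = 3.20, and (4 − 12 × 0.088)/√3.20 = 1.645.

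The separate counts are 6/12 and 2/12 in all three rows. If events fed and fasted were independent, the expected overlap would be 6 × 2/12 = 1, the middle row. An unpaired Newcombe 90% interval on the same counts is 1.7% to 57.4%.

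**3. Why an estimate and not a test**

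The exact two-sided McNemar p-value with k discordant pairs all in one direction is 2 × 0.5^k: 0.0625 for k = 5 and 0.031 for k = 6. At least six one-directional discordant pairs out of 12 would be needed. Assuming independence within pairs, power at two-sided 0.05 runs from about 4% (30% fasted, 10% fed) to 32% (50% fasted, 10% fed).

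**The case against.** The strongest reply is that this is a small Phase 1 study with an empirical sample size, no hypotheses and descriptive safety analysis, and that the SAP follows the formal objectives tables. Food is confounded with period and blinding, and possibly with dose, because doses in Periods 2 and 3 may be changed (Protocol 4.1, 4.3, 6.6). A paired interval removes none of this. At the expected overlap it is also close to the unpaired one (-0.3% to 59.8% against 1.7% to 57.4%). All of that stands. It limits the remedy to a labelled descriptive estimate. It does not explain why the stated reason for Period 3 has no matching analysis, and it leaves the unequal windows untouched.

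Three stronger readings are tempting, and the documents do not support them.

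- A reader might infer that the SAP looks at food for PK only and never sets fed and fasted AEs side by side. SAP 5.2 and Protocol 9.3.1 foresee separate summaries, and SAP 6.6.4 has a QTcF plot that refers to fed condition.
- A reader might infer that the pairing cannot be recovered. The sponsor standards are not available here and may include participant-level listings. What can be said is that no use of the pairing is prespecified.
- A reader might infer that this comparison will fix Phase 2/3 dosing instructions. Protocol 4.3 says only that data may be used that way, in its paragraph on optional Cohort 2.

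**Conclusion.** The point holds as a gap between the rationale in Protocol 4.2 and 4.3 on one side and the objectives tables and SAP on the other. There is no fed-versus-fasted tolerability objective, no GI outcome and no planned use of the within-participant pairing. The default AE counts are not comparable: at least 264 hours of attribution for A against about 144 for D. That follows from the documents' own schedule and applies to Cohort 1. How far it distorts the result depends on how many GI events start more than 48 hours after the last dose, which the documents do not say.

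The size of the pairing effect rests on assumed counts. With 6/12 and 2/12, the lower 90% limit moves between 9% and -6% on overlap alone, and is about zero at the overlap expected under independence. The interval is wide in every case. The change is worth making because it is cheap and answers a question the protocol itself asks, not because 12 pairs will settle it.

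**What to change.** 1. Add fed versus fasted GI tolerability as an objective and endpoint in Protocol 3 and SAP 2.2, so that they agree with Protocol 4.2 and 4.3.
2. In SAP 6.6.1 define the outcome as at least one TEAE in the GI system organ class from the first dose of the period to 48 hours after its last dose, ending before the first palatability tasting. This gives A and D the same window (96 + 48 = 144 h) and keeps the tastings out of D.
3. Report the A against D within-participant cross-tabulation (both, fed only, fasted only, neither) with the paired difference and a 90% score CI. Restrict it to participants who received the same dose in A and D, or flag those who did not.
4. Label the result descriptive, because D is always last and open label and the dose may differ.

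Cost: one objective row, one SAP paragraph and one small table, all from data already collected. The downside is a wide interval at n = 12, which the label should make plain. Paired tables against 200 mg or placebo and a separate antiemetic list are not needed for this point.

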## 6.6.2. Laboratory Data

Laboratory data will be listed and summarized by treatment in accordance with the sponsor reporting standards. Baseline is as defined in Section 3.5.2.

#### 6.6.3. Vital Signs

Vital signs data will be listed and summarized by treatment in accordance with the sponsor reporting standards.

Absolute values and changes from baseline in supine systolic blood pressure and pulse rate will be summarized by treatment and time postdose, according to sponsor reporting standards. Tables will be paged by parameter. Baseline is as defined in Section 3.5.3.

Mean changes from baseline for supine systolic blood pressure and pulse rate will be plotted against time post-dose. Each part will have its own output with 1 line for each treatment. Corresponding individual plots of changes from baseline will also be produced for each treatment.

Maximum decrease from baseline for supine systolic blood pressures and maximum increase from baseline for supine pulse rate will be summarized by treatment, according to sponsor reporting standards.

Minimum and/or maximum absolute values and changes from baseline for supine vital signs will also be summarized descriptively by treatment using categories as defined in Appendix 1. Numbers and percentages of participants meeting the categorical criteria will be provided. All planned and unplanned post-dose time points will be counted in these categorical summaries.

#### 6.6.4. Electrocardiograms

Changes from baseline for the ECG parameters HR, QTcF, PR interval, and QRS complex will be summarized by treatment and time. The frequency of uncorrected QT values above 500 ms will be tabulated.

The number (%) of participants with maximum postdose QTcF values and maximum increases from baseline in the following categories will be tabulated by treatment:

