4. STUDY DESIGN

4.1. Overall Design

This is a Phase 1 study that will be conducted in up to two cohorts.

Cohort 1 is a randomized, 2-part, crossover design. Part 1 has 3 periods, Periods 1 and 2 are double blind, sponsor open, placebo controlled crossover design to evaluate the safety and tolerability and PK of the planned 400 mg and 200 mg of sisunatovir given Q12 hours x 4 days plus 1 dose as 50 mg capsules in a fed state. Period 3, is an open label period to evaluate the food effect of the planned 400 mg of sisunatovir given Q12 hours x 4 days plus 1 dose in a fasted state. Part 2, Periods 4-7, is open label to assess the palatability of 50 mg of sisunatovir in 4 different vehicles (water, infant formula, apple juice, and saline) in a randomized crossover design.

Cohort 1 will include approximately 12 participants that will be randomized into 4 sequences with 3 participants in each sequence. Each sequence will receive treatment in a pre-specified manner ([Section 1.2 Schema](#)).

Participants will be admitted to the CRU on Day -1 to undergo baseline procedures. Over the first 2 periods, all participants are planned to receive (A) 400 mg and either (B) 200 mg plus matching placebo or (C) placebo dosed Q12 hours for 4 days plus 1 dose in the fed state. All participants in Period 3 will receive (D) 400 mg dosed Q12 hours for 4 days plus 1 dose in the fasted state. Note that the dose levels for Periods 2 and 3 are dependent upon the PK in the previous periods as described below.

Prior to proceeding to Period 2 of Cohort 1, the Period 1 Day 5 PK up to 12 hours post-dose will be assessed. If the mean exposures (AUC or Cmax) at 400 mg in Period 1 exceeds the rat (most sensitive species) NOAEL, the doses for the subsequent period(s) will be capped to a dose that is not expected to exceed the rat NOAEL. Similarly, prior to proceeding to Period 3 of Cohort 1, the Periods 1 and 2 Day 5 PK up to 12 hours post-dose will be assessed, and if the mean exposures (AUC or Cmax) at 400 mg exceeds the rat (most sensitive species) NOAEL, the doses for the subsequent period(s) will be capped to a dose that is not expected to exceed the rat NOAEL. Furthermore, safety will also be assessed following each period and doses for subsequent periods may be reduced if the safety and tolerability of the previous dose was not deemed sufficiently tolerated.

A minimum 7-day washout period will occur between the last dose of Periods 1 and 2 and the first dose of Periods 2 and 3.

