5.3.2. Meals and Dietary Restrictions

- Participants must abstain from all food and drink (except water) at least 4 hours prior to any safety laboratory evaluations.
- On Dosing days in periods 1 and 2, participants will consume a standard meal approximately 30 minutes prior to dosing. They should be encouraged to complete their meals on Day 1 and Day 5 (PK sampling days) by approximately 10 minutes prior to anticipated dosing.
- During Period 3, lunch will be the first meal after an overnight fast of approximately 10 hours.
- During the palatability assessment periods, there will be at least 60 minutes between meals and palatability assessments.

- Lunch will be provided approximately 4 hours after dosing.
- In Period 3, dinner will be provided approximately 13 hours after AM dosing (1 hour after PM dosing).
- In Period 3, an afternoon snack may be permitted approximately 7.5 hours after AM dosing.
- An evening snack may be permitted, for all periods.
- Participants will refrain from consuming red wine, grapefruit, or grapefruit-related citrus fruits (eg, Seville oranges, pomelos, fruit juices) from 7 days prior to the first dose of study intervention until collection of the final PK blood sample.
- While participants are confined, their total daily nutritional composition should be approximately 55% carbohydrate, 30% fat, and 15% protein. The daily caloric intake per participant should not exceed approximately 3200 kcal.

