8.3.3. Electrocardiograms

Standard 12-lead ECGs utilizing limb leads (with a 10-second rhythm strip) should be collected at times specified in the [SoA](#) section of this protocol using an ECG machine that automatically calculates the HR and measures PR interval, QT interval, QTcF, and QRS complex. Alternative lead placement methodology using torso leads (eg, Mason-Likar) should not be used given the potential risk of discrepancies with ECGs acquired using standard limb lead placement. All scheduled ECGs should be performed after the participant has rested quietly for at least 5 minutes in a supine position.

3 baseline pre-dose measurements are needed for CQT analysis, these ECGs will be done approximately 30 min, 20 min, and 10 min before the pre-dose meal in Periods 1 and 2, and approximately 30 min, 20 min, and 10 min pre-dose in Period 3. The average of the triplicate ECGs over the 3 pre-dose measurements (total of 9 ECGs) will serve as each participant's baseline QTc value. Triplicate 12-lead ECGs will be obtained approximately 2 to 4 minutes apart.

To ensure safety of the participants, a qualified individual at the investigator site will make comparisons to baseline measurements. Additional ECG monitoring will occur if a) a postdose QTcF interval is increased by ≥ 60 ms from the baseline **and** is > 450 ms; or b) an absolute QT value is ≥ 500 ms for any scheduled ECG. If either of these conditions occurs, then 2 additional ECGs will be collected approximately 2 to 4 minutes apart to confirm the original measurement. If the QTcF values from these repeated ECGs remain above the threshold value, then a single ECG must be repeated at least hourly until QTc values from 2 successive ECGs fall below the threshold value that triggered the repeat measurement.

To ensure safety of the participants, a qualified individual at the investigator site will make comparisons to baseline measurements. Additional ECG monitoring will occur if a) the mean value from the triplicate measurements for any postdose QTcF interval is increased by ≥ 60 ms from the baseline **and** is > 450 ms; or b) an absolute QT value is ≥ 500 ms for any scheduled ECG. If either of these conditions occurs, then a single ECG measurement must be repeated at least hourly until QTcF values from 2 successive ECGs fall below the threshold value that triggered the repeat measurement.

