## 3.5.4. Electrocardiograms

A 12-lead ECG will be obtained on all participants at screening. 12-lead ECGs will be recorded on all participants at times detailed in the SoA given in the protocol. Triplicate measurements will be performed.

The QT, QTcF, PR, QRS and heart rate (HR) will be recorded at each assessment time. The average of the triplicate readings collected (where applicable) at each assessment time will be calculated for each ECG parameter. If not supplied, QTcF will be derived using Fridericia's heart rate correction formula:

QTcF = QT / (RR)
$$^(1/3)$$
 where RR = 60/HR (if not provided)

For Periods 1 to 3, the baseline value is the average of the triplicate ECG measurements collected before dose administration on Day 1 in each period. Changes from baseline will be defined as the change between the average of the postdose triplicate ECG measurements and the baseline ECG.

The following ECG endpoints will be determined:

- Change from baseline in QT interval, heart rate, QTcF interval, PR interval, and QRS complex.
- The maximum absolute value (post-dose) will be calculated for QTcF, PR and QRS.
- The maximum increase from baseline over all measurements taken post-dose will be calculated for QTcF.

The maximum increase from baseline will be calculated by first subtracting the baseline value from each postdose measurement to give the change from baseline. The maximum of these values over the respective period will then be selected, except in the case where a participant does not show an increase. In such an instance, the minimum decrease should be taken.

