## Safety QTcF Assessment

Degree of	Mild (ms)	Moderate (ms)	Severe (ms)
Prolongation			
Absolute value	>450-480	>480-500	>500
Increase from		$> 30 \text{ and} \le 60$	>60
baseline			

If more than 1 ECG is collected at a nominal time after dose administration (for example, triplicate ECGs), the mean of the replicate measurements will be used to represent a single observation at that time point. If any of the 3 individual ECG tracings has a QTcF value >500 ms, but the mean of the triplicates is not >500 ms, the data from the participant's individual tracing will be described in a safety section of the CSR in order to place the >500 ms value in appropriate clinical context. However, values from individual tracings within triplicate measurements that are >500 ms will not be included in the categorical analysis unless the average from the triplicate measurements is also >500 ms.

Absolute values and changes from baseline in QT, heart rate, QTcF, PR and QRS will be summarized by treatment and time post-dose using sponsor reporting standards. Tables will be paged by parameter. Baseline is as defined in Section 3.5.4.

Mean changes from baseline in QT, heart rate and QTcF will be plotted against time postdose. Each period will have its own output with 1 line for each treatment. Corresponding individual plots of changes from baseline will also be produced for each treatment.

Changes from baseline in QTcF will also be plotted separately against drug concentrations of sisunatovir and fed condition. This will be a scatter plot for all observations where QTcF and drug concentration are recorded. Placebo data will also be included (with drug concentration set to zero). Different symbols will be used for each treatment.

Maximum increase from baseline for QTcF will be summarized by treatment, according to sponsor reporting standards.

ECG endpoints and changes from baseline (QTcF, PR and QRS) will also be summarized descriptively by treatment using categories as defined in Appendix 1 (for QTcF these correspond to the Pfizer Guidance in Section 8). Numbers and percentages of participants meeting the categorical criteria will be provided. All planned and unplanned postdose time points will be counted in these categorical summaries.

Listings of participants with any single post-dose value >500 msec will also be produced for QTcF.

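### The SAP plans no placebo-adjusted ECG change with a confidence interval, so with a pre-meal baseline the fed 400 mg and 200 mg changes cannot separate drug from meal and time of day

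*SAP*

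**What the plan says.** Protocol section 4.1 describes Cohort 1 as follows: "Periods 1 and 2 are double blind, sponsor open, placebo controlled crossover design". Section 4.2 sets 400 mg (n=12) against 200 mg (n=6) and placebo (n=6), all fed. Period 3 gives fasted 400 mg (Treatment D) to everyone, with no placebo.

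For the fed periods, Protocol section 8.3.3 says of the baseline recordings: "these ECGs will be done approximately 30 min, 20 min, and 10 min before the pre-dose meal in Periods 1 and 2". For the fasted period they are taken "approximately 30 min, 20 min, and 10 min pre-dose in Period 3". Section 5.3.2 places the meal in Periods 1 and 2: "participants will consume a standard meal approximately 30 minutes prior to dosing". SAP section 3.5.4 uses these recordings as the reference: "the baseline value is the average of the triplicate ECG measurements collected before dose administration on Day 1 in each period".

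SAP section 6.6.4 then plans: "Changes from baseline for the ECG parameters HR, QTcF, PR interval, and QRS complex will be summarized by treatment and time". It also plans: "Absolute values and changes from baseline in QT, heart rate, QTcF, PR and QRS will be summarized by treatment and time post-dose". Further outputs are maximum values and changes, categorical counts, mean-change plots (a separate output per period, one line per treatment), and a scatter of QTcF change against concentration with placebo entered at zero. For vital signs, section 6.6.3 has the parallel text: "Absolute values and changes from baseline in supine systolic blood pressure and pulse rate will be summarized by treatment and time postdose".

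No active-minus-placebo difference, interval or model for ECG or vital signs appears in the unredacted text of either document.

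**The concern.** A fed change from baseline runs from a pre-breakfast recording to one made after breakfast and later in the day. Whatever breakfast and the clock do to heart rate and QTcF is therefore included in the 400 mg and 200 mg figures. The fed placebo period carries the same meal and timetable, so it is the natural correction, and the crossover supplies it within person for six participants. The planned tables leave readers to make that subtraction by eye, with no measure of its uncertainty.

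ECG is part of the primary endpoint, and Protocol section 4.2 says 400 mg is slightly above the highest multiple dose tested before (350 mg). A meal effect could hide a drug effect on QTcF or heart rate, or be mistaken for one.

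**Working it through.** **1. Participants available.** The schema figure is not shown, so sequences AB, BA, AC and CA (A = 400 mg fed, B = 200 mg fed, C = placebo fed) with 3 participants each are assumed. This gives A = 4 × 3 = 12, B = 2 × 3 = 6 and C = 2 × 3 = 6, which reproduces the 12, 6 and 6 in Protocol section 4.2. Six people have both A and C, six have both A and B, and none has both B and C. The plan gives no precision or power figure for ECG to reproduce.

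**2. Where the baseline sits.**
- Periods 1-2: the meal starts about 30 min before dosing, so the baseline ECGs fall about 30+30 = 60, 30+20 = 50 and 30+10 = 40 min before the dose, with the meal in between.
- Period 3: they fall 30, 20 and 10 min before the dose, with no meal in between. Lunch comes about 4 h after dosing.
- Day 5, hour 0, Periods 1-2: the notes to Protocol Table 2 also place this ECG before the meal. It follows eight doses and matches the Day 1 baseline in clock time and food state, so breakfast does not affect it.

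**3. What each figure estimates after the morning dose.**
- Fed active change = drug + (meal and time of day)
- Fed placebo change = (meal and time of day)
- Difference = drug

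This holds whatever the size of the shift. An illustration with assumed sizes: a drug effect of +10 ms and a shift of -10 ms give a raw change of 0 ms and a placebo-adjusted change of 10 ms. A drug effect of 0 and a shift of +5 ms give a raw change of 5 ms and an adjusted change of 0 ms.

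**4. Precision of the correction.** The model is change = treatment + period + random participant, at one time point, Periods 1-2. The SDs are assumptions: between-participant sb = 4-6 ms and within-participant sw = 6-8 ms. With s² = sb² + sw² and r = sb²/s², generalized least squares for this layout gives:
- Var(A−C) = s²(1−r)(3+r)/12
- Var(B−C) = s²(1−r²)/3

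Degrees of freedom are 24 observations − 12 participants − 1 period − 2 treatment = 9, and t(0.95, 9) = 1.833.

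| sb, sw (ms) | s² | r | SE(A−C) | 90% half-width | SE(B−C) | 90% half-width |
|---|---|---|---|---|---|---|
| 4, 6 | 52 | 0.308 | 3.15 | 5.8 | 3.96 | 7.3 |
| 6, 6 | 72 | 0.500 | 3.24 | 5.9 | 4.24 | 7.8 |
| 6, 8 | 100 | 0.360 | 4.23 | 7.8 | 5.39 | 9.9 |

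First row for A−C: 52 × 0.692 × 3.308 / 12 = 9.92; √9.92 = 3.15; 1.833 × 3.15 = 5.8 ms.

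**5. Bias against variance.** The uncorrected mean for A has SE √(s²/12); at SDs (6, 8) this is √(100/12) = 2.89 ms. With an assumed shift of 3 ms its root mean squared error is √(8.33 + 9) = 4.2 ms, about the same as the corrected 4.2 ms. With a shift of 8 ms it is √(8.33 + 64) = 8.5 ms against 4.2 ms.

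**The case against.** The strongest reply is that the study is descriptive. It tests no hypothesis, its sample size is empirical, and placebo is tabulated at the same nominal times under the same fed conditions, so the comparison is open to any reader. The protocol also mentions concentration-QT analysis, and sponsor reporting standards not shown here may add outputs.

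Part of this stands. A reader might infer that ECG results come only as raw change and that placebo is ignored. The documents do not support that: absolute values, maxima, categories and a scatter that includes placebo are all planned. The adjusted intervals are also wide, and step 5 shows that with a small shift the correction gains nothing in total error.

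The reply does not remove the gap. The same SAP gives 90% intervals for the food effect (section 6.2.2) and palatability (section 6.2.3), so a descriptive interval for a primary safety endpoint fits its approach. The mean-change plots are split by period. Under the assumed sequences that leaves about three placebo participants per output and puts each person's active and placebo data in different outputs. Protocol section 4.2 calls concentration-QTc modelling only possible, and the visible SAP specifies just the scatter.

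Two further readings go too far:
- **Barring the fed-versus-fasted comparison.** Protocol sections 4.2 and 4.3 call for comparing safety and tolerability between the two. The difference in meal anchoring mainly affects times up to lunch at about 4 h; after lunch, fasted 400 mg is also post-meal against a fasted baseline. The scatter already uses a different symbol for each treatment.
- **Extending the pre-meal argument to blood pressure and pulse rate.** SAP section 3.5.3 says only that their baseline is pre-dose on Day 1; its timing relative to the meal is not stated.

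**Conclusion.** The point holds in limited form. In the visible text, no placebo-adjusted ECG change with an interval is specified, although the design supplies a fed placebo and six within-person pairs for 400 mg. Because the Period 1-2 baseline precedes the meal, the fed 400 mg and 200 mg changes after the morning dose cannot on their own separate drug from meal and time of day. The Day 5 hour-0 ECG is an exception as regards the meal.

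That mixing follows from the schedule and needs no outside figure. Its size is unknown: the 3-8 ms shift used above is an assumption, as are the SDs. On those SDs the 90% half-width is about 5.8-7.8 ms for 400 mg minus placebo and 7.3-9.9 ms for 200 mg minus placebo, the latter resting largely on different participants. For fasted 400 mg there is no matching placebo, so an A-versus-D difference in ECG change cannot be attributed to drug alone.

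**What to change.** In SAP section 6.6.4, for Periods 1-2 and at each nominal time, add the active-minus-placebo difference in change from baseline with a 90% CI for QTcF and heart rate; PR and QRS are optional. Use a mixed model with treatment and period as fixed effects and participant as a random effect. Define treatment by the dose actually administered, as SAP section 5.2 already does for summaries, because Period 2 doses may be reduced. Label the output descriptive, and state that the intervals are wide and that 200 mg minus placebo is largely a between-participant contrast.

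Keep the planned A-versus-D comparison. Add a note that the two ECG baselines stand in different relation to food, mainly affecting times up to about 4 h, and that there is no fasted placebo.

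In section 6.6.3 the same placebo difference may be added for vital signs as a descriptive output, without the pre-meal argument.

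The cost is SAP wording and a few outputs, with no new data. Protocol Table 2 gives about 20 on-treatment ECG times, so two parameters and two contrasts mean about 20 × 2 × 2 = 80 intervals. They should be read as a profile over time, not one by one.
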